### **9.6 EFFICACY**

#### **9.6.1 Definition of Efficacy Endpoints**

The primary efficacy endpoint is the objective response rate (ORR). ORR is defined as the proportion of patients who have a best overall response (BOR) of CR or PR as determined using RECIST v1.1 or modified MDA criteria for bone-exclusive disease (see [Table 11](#)). BOR is defined as the best response recorded between the date of first dose of investigational product and the date of subsequent anti-cancer therapy. A BOR of CR or PR requires confirmation of the assessment at least 4 weeks later.

Other efficacy endpoints are as follows:

Confidential

Document State: Effective (Controlled)  
CONFIDENTIAL

Page 83 of 118

- DOR, defined as the interval from the first documentation of CR or PR to the earlier of the first documentation of disease progression (per RECIST v1.1) or death from any cause.
- PFS, defined as the interval from the start of investigational product to the earlier of the first documentation of disease progression or death from any cause
- OS, defined as the time from the date of start of treatment to the date of death from any cause. Patients who are lost to follow-up and those not known to have died by the cut-off date for analysis will be censored on the date the patient was last known alive, or the data cut-off date, whichever is earlier.

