Paired tumor biopsies will be collected at screening (fresh or archival5 within 3 years) and on treatment at Cycle 4 Day 1 ±28 days provided medically safe and not contraindicated. Samples will be sent to a central vendor for NGS analysis. Tumor Formalin-fixed paraffin embedded (FFPE) slides will be evaluated by IHC for NICD1 stain. On the day of the on-treatment biopsy, blood will also be drawn for PK and biomarker assessments.

During the Treatment period, patients will undergo radiographic assessments every 8 weeks (±3 days) for review by the Investigator. Scans will be collected and held for possible future retrospective evaluation by independent central review (ICR). Other assessments will be done as specified in Schedule of Activities (SoA; Table 1), including safety and exploratory biomarkers.

A repeat of tumor imaging will be required for the purposes of confirmation of response (i.e., partial response, and/or complete response). The confirmation scan should be no earlier than 4 weeks following the first indication of response.

All patients will undergo end of study (EOS) visit 30 days post last treatment and be contacted by phone every 3 months to determine survival status. In patients who discontinued investigational product due to toxicity, radiographic imaging will be done

every 3 months until disease progression or until patient initiates another anti-cancer therapy.

Study participation for each patient consists of:

- Screening period: up to 28 days
- Treatment period: Weekly treatment, until disease progression⁶, unacceptable toxicity, or consent withdrawal
- EOS: 30 days after the last administration of investigational product.
- Long term follow-up: Every 3 months.

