6.4 Efficacy and Safety Variables

6.4.1 *Description of Efficacy Variables*

6.4.1.1 *Primary Efficacy Variables*

The primary efficacy endpoint is the objective response rate (ORR).

ORR is defined as the proportion of subjects who have a best overall response (BOR) of complete response (CR) or partial response (PR) as determined by Investigator review

using RECIST v1.1 (Protocol Appendix C) or modified MDA bone criteria for subjects with bone-exclusive disease (Protocol Appendix C, Table 11).

BOR is defined as the best response recorded between the date of first infusion of investigational product and the date of subsequent anti-cancer therapy. A BOR of CR or PR requires confirmation of the assessment at least 4 weeks later. A BOR of SD requires the assessment to be recorded no less than 4 weeks after the start of study medication.

RECIST 1.1 (Eisenhauer 2009) will be used to determine response at each post-baseline time point. Assessment of target lesions, non-target lesions, new lesions, and overall response will be assigned as described in Table 3, Table 4 and Table 5. Table 6 describes the derivation of best overall response from overall response assessments at each visit.

Table 3 RECIST 1.1 Evaluation of Target Lesions:

Response	Definition
CR	Disappearance of all target lesions. Any pathological lymph nodes must have reduction in short axis to < 10 mm.
PR	At least a 30% decrease in the sum of the diameters of target lesions, taking as reference the baseline sum diameters.
PD	At least a 20% increase in the sum of the diameters, taking as reference the smallest sum on study (this includes the baseline sum if that is the smallest on study). In addition to the relative increase of 20%, the sum must also demonstrate an absolute increase of at least 5 mm. The appearance of one or more new lesions is also considered progression.
SD	Neither sufficient shrinkage to qualify for PR nor sufficient increase to qualify for PD, taking as reference the smallest sum diameters on study.

Table 4 RECIST 1.1 Evaluation of Non-target Lesions:

Response	Definition
CR	Disappearance of all non-target lesions and normalization of tumor marker level. All lymph nodes must be non-pathological in size (< 10 mm short axis).
SD	Persistence of one or more non-target lesion(s) or/and maintenance of tumor marker level above the normal limits.
PD	Appearance of one or more new lesions and/or unequivocal progression of existing non-target lesions.

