6.4.1.2 Secondary Efficacy Variables

Secondary efficacy endpoints include the following:

Duration of Response (DOR): defined as the time interval from the initial confirmed response of CR or PR to the earlier of the first documentation of disease progression (per RECIST v1.1 or modified MDA criteria) or death from any cause, as determined by Investigator review. DOR will be calculated in months as (date of disease progression or death/censoring – date of initial response + 1) / 30.4375.

For DOR (and PFS) the date of progression or death and censoring will be based on the Food and Drug Administration (FDA) guidance *Clinical Trial Endpoints for the Approval of Cancer Drugs and Biologics* (May 2007), as defined in Table 7.

Table 7 Determining Date of Progression or Censoring for PFS and DOR Analysis

Situation	Date of Progression or Censoring	Outcome
Alive and without documentation of disease progression.	Date of last disease assessment. All patients still alive and without documentation of disease will be censored as of July 31, 2022.	Censored
Treatment discontinuation for undocumented progression	Date of last disease assessment	Censored
Treatment discontinuation for toxicity or other reason	Date of last disease assessment	Censored
Other anticancer treatment started before documentation of disease progression or death	Date of last disease assessment prior to start of other anticancer treatment	Censored

Death before first disease assessment	Date of death	Progressed
Death or disease progression between planned disease assessments	Date of death or first disease assessment showing disease progression, whichever occurs first	Progressed
Death or progression after more than one missed disease assessment	Date of last disease assessment visit without documentation of disease progression that is before the first missed visit	Censored

As part of the sensitivity analysis, DOR will also be derived as follows:

- As above but where confirmation of PR/CR is not required.
- As above but based on central review rather than Investigator review.
- As above but based on central review rather than Investigator review and where confirmation of PR/CR is not required.

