Progression-Free Survival (PFS): defined as the interval from the start of investigational product to the earlier of the first documentation of disease progression (per RECIST v1.1 or modified MDA criteria) or death from any cause, as determined by Investigator review. Progression-free survival will be defined in months as: (date of progression or death/censoring – date of first infusion + 1) / 30.4375.

Patients without disease progression or death will be censored as per Table 7.

As part of the sensitivity analysis, PFS will also be derived as follows:

- As above but based on central review rather than Investigator review.

Overall Survival (OS): defined as the time from the date of start of treatment to the date of death from any cause. Subjects with no documentation of death will be censored at the last date known to be alive, per the data collection. Sites will be asked to search public registries for any possible death dates for subjects who withdrew consent from the study (as per FDA Guidance for Sponsors, Clinical Investigators, and IRBs

Data Retention When Subjects Withdraw from FDA-Regulated Clinical Trials). Where it is possible for this search to be done, any deaths found will be included in the analysis. Overall survival time will be calculated in months as (date of death/censoring – date of first infusion + 1) / 30.4375.

As part of the sensitivity analysis, OS will also be derived as follows:

- As above but where date of first diagnosis of recurrent or metastatic disease is used instead of date of first infusion.
- As above but where date of initial ACC diagnosis is used instead of date of first infusion.

Time to Response (TTR): defined as the interval from the start of investigational product to the initial (subsequently confirmed) response of CR or PR (per RECIST v1.1 or modified MDA criteria), as determined by Investigator review. TTR will be calculated in months as $(\text{date of initial response/censoring} - \text{date of first infusion} + 1) / 30.4375$.

Patients without response will be right censored at their last tumor assessment.

As part of the sensitivity analysis, TTR will also be derived as follows:

- As above but where confirmation of PR/CR is not required.
- As above but based on central review rather than Investigator review.
- As above but based on central review rather than Investigator review and where confirmation of PR/CR is not required.

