7.5.3.1 Duration of Response

The Kaplan-Meier method will be used to analyze DOR. The Kaplan-Meier curves will be plotted. Counts and percentages for number of subjects who experienced the event of interest and those who are censored will be presented along with minimum and maximum duration in months. The median, 25th and 75th percentiles will be estimated and their corresponding Brookmeyer-Crowley 95% CIs using the Kaplan-Meier estimates. Landmark estimates will be provided for 2, 4, 6 and 8 months after start of investigational product.

The following sensitivity analyses will be conducted:

- The DOR analysis will be repeated using the PP analysis set;
- The DOR analysis will be repeated using unconfirmed response;
- The DOR analysis will be repeated using central read based on confirmed response;

□

The DOR analysis will be repeated using central read based on unconfirmed response.

Subgroup analyses will not be performed for DOR due to the small number of responders.

DOR will be displayed graphically by patient and cohort using swimmer plots.

7.5.3.2 *Progression Free Survival*

PFS will be summarized similarly to DOR using the Kaplan-Meier method and estimates will be presented along with Brookmeyer-Crowley 95% CIs. Appropriate landmark estimates will also be included.

The following sensitivity analyses will be conducted:

- The PFS analysis will be repeated using the PP analysis set;
- The PFS analysis will be repeated using central read;
- The PFS analysis will be repeated using the subset of subjects with a BOR of PR (BOR will be based on the Investigator results irrespective of confirmation; PFS will be based on the Investigator results).

Subgroup analyses will also be performed based on the main subgroups outlined above for ORR. Kaplan-Meier curves will be plotted for each subgroup.

7.5.3.3 *Overall Survival*

OS will be summarized similarly to DOR using the Kaplan-Meier method and estimates will be presented along with Brookmeyer-Crowley 95% CIs. Appropriate landmark estimates will also be included.

The following sensitivity analyses will be conducted:

- The OS analysis will be repeated using the PP analysis set;
- The OS analysis will be repeated using the Safety analysis set;
- The OS analysis will be repeated using the subset of subjects with a BOR of PR (BOR will be based on the Investigator results irrespective of confirmation).

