Additional analyses of OS will be conducted using the same methods as outlined above, with the following changes to the definition of OS:

□

Calculated using date of first recurrent or metastatic disease instead of date of first infusion as time 0 (the same rules as detailed in Section 7.4.3 will be used to impute partial dates and in some cases, missing, dates);

- Calculated using date of initial ACC diagnosis instead of date of first infusion as time 0 (the same rules as detailed in Section 7.4.3 will be used to impute partial dates).

Subgroup analyses will also be performed based on the main subgroups outlined above for ORR. Kaplan-Meier curves will be plotted for each subgroup.

7.5.3.4 *Time to Response*

TTR will be summarized similarly to DOR using the Kaplan-Meier method and estimates will be presented along with Brookmeyer-Crowley 95% CIs. Appropriate landmark estimates will also be included.

The following sensitivity analyses will be conducted:

- The TTR analysis will be repeated using the PP analysis set;
- The TTR analysis will be repeated using unconfirmed response;
- The TTR analysis will be repeated using central read based on confirmed response;
- The TTR analysis will be repeated using central read based on unconfirmed response.

Subgroup analyses will also be performed based on the main subgroups outlined above for ORR. Kaplan-Meier curves will be plotted for each subgroup.

7.5.3.5 *Disease Control Rate*

DCR will be summarized similarly to ORR.

The following sensitivity analyses will be conducted:

- The DCR analysis will be repeated using the PP analysis set;
- The DCR analysis will be repeated using unconfirmed response;
- The DCR analysis will be repeated using central read based on confirmed response;

□

The DCR analysis will be repeated using central read based on unconfirmed response.

Subgroup analyses will also be performed based on the main subgroups outlined above for ORR. The results will be displayed graphically in forest plots.

7.5.3.6 *Change in EORTC QLQ-C30*

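### The SAP times the duration-of-response landmarks from start of treatment, although duration of response starts at the initial response (minor, wrong as written)

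*SAP*

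**What the plan says.** The DOR analysis section (SAP 7.5.3.1) asks for a Kaplan-Meier curve, median, quartiles and range, and then adds: "Landmark estimates will be provided for 2, 4, 6 and 8 months after start of investigational product".

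The endpoint definition uses a different time origin. SAP 6.4.1.2 describes DOR in these words: "defined as the time interval from the initial confirmed response of CR or PR to the earlier of the first documentation of disease progression". A fatal outcome also ends the interval, and the formula there subtracts the date of initial response. Protocol 9.6.1 agrees: "DOR, defined as the interval from the first documentation of CR or PR to the earlier of the first documentation of disease progression". There too, a fatal outcome is the other possible end.

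Start of treatment is the origin of another endpoint in the same SAP section, progression-free survival (PFS), which is described in these words: "defined as the interval from the start of investigational product to the earlier of the first documentation of disease progression". Again a fatal outcome is the alternative end.

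Two further statements fix when a response can begin and be confirmed. SAP 6.1 says that "patients will undergo radiographic assessments every 8 weeks", with a window of 3 days either side. SAP 6.4.1.1 says: "A BOR of CR or PR requires confirmation of the assessment at least 4 weeks later".

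**The concern.** One endpoint has two clocks. A DOR landmark is normally the estimated proportion of responders still in response a given time after they responded. Patients respond at different scans, so a fixed time after first infusion is a different point in each patient's response, and for late responders it comes before the response exists. Neither document reconciles the two origins.

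What is at stake is the meaning and the label of four secondary estimates. If a programmer follows the sentence, the figures are not durations of response. If the programmer reads the estimates from the DOR curve instead, the output departs from the SAP sentence, and a table title copied from that sentence would be wrong.

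**Working it through.** The plan states no DOR assumption and no landmark result, so there is no figure of its own to reproduce. The check places the four landmarks on the DOR clock.

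**Inputs**
- Landmarks: 2, 4, 6 and 8 months after start of treatment (SAP 7.5.3.1).
- Scans: every 8 weeks, ±3 days (SAP 6.1).
- Confirmation: at least 4 weeks, or 28 days, after the first response (SAP 6.4.1.1).
- Month: 30.4375 days (SAP 6.4.1.2 and 7.1.5).

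**Step 1: when responses begin.** Elapsed time from first infusion is days / 30.4375:
- week 8: 56 / 30.4375 = 1.84 months
- week 16: 112 / 30.4375 = 3.68 months
- week 24: 168 / 30.4375 = 5.52 months
- week 32: 224 / 30.4375 = 7.36 months

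**Step 2: where the landmarks fall.** Time in response = landmark − start of response. The one-day increment in the SAP formulas enters both clocks and cancels.

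| Response first seen | 2 months | 4 months | 6 months | 8 months |
|---|---|---|---|---|
| Week 8 | 0.16 | 2.16 | 4.16 | 6.16 |
| Week 16 | −1.68 | 0.32 | 2.32 | 4.32 |
| Week 24 | −3.52 | −1.52 | 0.48 | 2.48 |
| Week 32 | −5.36 | −3.36 | −1.36 | 0.64 |

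A negative entry means that the patient has not yet responded.

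**Step 3: what the 2-month landmark can show.** Two months is 2 × 30.4375 = 60.9 days. The week-8 scan falls on days 53 to 59, so the landmark comes 1.9 to 7.9 days after it. A response needs at least 28 days to be confirmed, so a confirmed week-8 responder is still in response at the landmark by definition. Every responder first seen at week 16 (days 109 to 115) or later has not yet responded. No confirmed responder found at a scheduled scan can therefore supply durability information at this landmark.

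**Step 4: the other landmarks.** The same comparison applies to the latest group that has responded by each landmark:
- 4 months = 121.75 days, which is 6.8 to 12.8 days after a week-16 scan. It is informative only for week-8 responders.
- 6 months = 182.6 days, which is 11.6 to 17.6 days after a week-24 scan. It is informative only for week-8 and week-16 responders.
- 8 months = 243.5 days, which is 16.5 to 22.5 days after a week-32 scan. It is informative only for responders first seen at weeks 8 to 24.

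**Step 5: the unconfirmed sensitivity version.** The confirmation argument does not apply here. However, the next scheduled scan after week 8 is no earlier than day 109, so at 60.9 days only a death or an off-schedule scan could have ended a response. The 2-month landmark is nearly empty in this version too.

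**Step 6: the other reading of the DOR start.** If the SAP definition were taken to start DOR at the confirming scan, a week-8 responder would start no earlier than (56 + 28) / 30.4375 = 2.76 months. The 2-month landmark would then precede that start by at least 0.76 month. The mismatch does not depend on which reading is taken.

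**The case against.** The strongest reply is that this is a slip of wording. SAP 6.4.1.2 fixes the DOR variable by formula, and SAP 7.5.3.1 applies Kaplan-Meier to that variable, so any landmark has to be read from a curve whose axis starts at response. The negative entries in the table show that the literal rule has no sensible implementation on that variable. On this view the likely harm is a wrong label, on a secondary descriptive endpoint for which the SAP itself expects few responders.

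Most of this stands, and it is why the point is minor. It does not remove the contradiction. SAP section 4 gives the SAP precedence over the protocol, says that it exists to prevent choices made after the fact, and requires departures from it to be recorded in the study report. Its own sentence should not have to be overridden silently to obtain a meaningful estimate.

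A reader might infer two wider problems that the documents do not support:
- **Landmarks for the other time-to-event endpoints.** SAP 7.5.3.2 says "PFS will be summarized similarly to DOR using the Kaplan-Meier method" and SAP 7.5.3.4 says "TTR will be summarized similarly to DOR using the Kaplan-Meier method", so the wrong origin might seem to spread. It does not. SAP 6.4.1.2 defines PFS, overall survival and time to response from treatment start, with formulas. SAP 7.5.3.3 states time 0 for the two additional survival analyses. Each section also asks for its own suitable landmarks.
- **Responses after progression.** The best-response window ends only at subsequent anti-cancer therapy, so progression might seem able to precede the start of DOR. That is a separate question. The answer depends on the published RECIST v1.1, which both documents cite and which is not available here. SAP Table 6 has no row that begins with progression, but it has none that begins with stable disease either, so its silence proves little. Scheduled treatment-period imaging stops at progression, and the number of patients affected is unknown.

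**Conclusion.** The landmark sentence in SAP 7.5.3.1 is wrong as written. It conflicts with the DOR definition in SAP 6.4.1.2 and in protocol 9.6.1, and nothing in either document resolves the conflict. Confidence in the textual mismatch is high.

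The consequence is minor. Only the four landmark estimates and their label are affected, and they are descriptive. It would be wrong to conclude that the DOR results as a whole are biased, because the other DOR summaries use the formula with the correct origin. Objective response rate, sample size and power are untouched.

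The offsets assume that responses are first seen at scheduled scans; a response found off schedule would shift them. No change in the estimated percentages is offered, because the documents give no DOR distribution and any such figure would rest on an assumed one.

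**What to change.** In SAP 7.5.3.1, keep the four times and replace the reference to start of investigational product with *the date of initial response*. Label the landmark rows in the DOR tables in the same way. The phrase also serves the unconfirmed and central-read versions, since each has its own date of initial response.

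The cost is one phrase and one table label. No new data, new analysis or change to any other endpoint is needed. If the SAP can no longer be amended, the correction can be recorded in the study report, as SAP section 4 already provides for departures from the plan.

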7.5 Efficacy Evaluation

7.5.1 *Datasets Analyzed*

All efficacy summaries will be based on the Efficacy Evaluable analysis set (central version for central read outputs) and will be repeated using the PP analysis set for the primary version of each endpoint (the primary version of each endpoint is the first version of the endpoint detailed in each of the sections below, i.e. ORR based on confirmed – local assessment is the primary version of ORR). OS data will also be repeated using the Safety analysis set. A data listing of subjects excluded from any analysis set, to include the reason for exclusion, will be presented.

All efficacy figures will display AL101 4 mg, AL101 6 mg and the total (combined) groups on separate pages.

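### OS counted from recurrent/metastatic disease or from initial diagnosis uses ordinary Kaplan-Meier although every subject had to survive to first infusion; drop these curves or label them conditional

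*SAP*

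**What the plan says.** **OS from an earlier origin.** SAP 6.4.1.2 defines OS from first infusion and then says: "As part of the sensitivity analysis, OS will also be derived as follows". The first variant reads: "As above but where date of first diagnosis of recurrent or metastatic disease is used instead of date of first infusion". The second uses the date of initial ACC diagnosis. SAP 7.5.3.3 repeats both under another name: "Additional analyses of OS will be conducted using the same methods as outlined above", with time 0 as "Calculated using date of first recurrent or metastatic disease instead of date of first infusion as time 0" and "Calculated using date of initial ACC diagnosis instead of date of first infusion as time 0". The methods outlined above are Kaplan-Meier with Brookmeyer-Crowley intervals. Neither document mentions delayed entry or a conditional reading.

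**Who is in the data.** Under SAP 7.2 the Safety set needs at least one infusion, complete or partial. The Efficacy Evaluable set needs a complete infusion and a post-baseline tumour assessment.

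**Responder repeats.** Among the sensitivity analyses, SAP 7.5.3.2 lists "The PFS analysis will be repeated using the subset of subjects with a BOR of PR" and SAP 7.5.3.3 lists "The OS analysis will be repeated using the subset of subjects with a BOR of PR". Both take the Investigator's response irrespective of confirmation.

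**Related text.** SAP 7.5.1 adds: "OS data will also be repeated using the Safety analysis set". SAP 7.4.3 will summarise time from initial diagnosis, and from first recurrent or metastatic disease, to first infusion.

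**The concern.** A Kaplan-Meier curve estimates survival from its time origin only if subjects could be seen to fail from that origin onwards. Here they could not. A patient who died between diagnosis and infusion never entered the trial, while each patient who did enter is counted as having been at risk, and surviving, through that whole interval. The early part of the curve is therefore flat by construction and the median moves right.

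The stake is interpretation. Protocol 1.1 itself cites survival of about 80%, 60% and 45% at 5, 10 and 15 years after resection, and a reader may well set a curve from initial diagnosis beside such figures. Calling the analysis a sensitivity analysis in one section and an additional analysis in another also leaves its purpose unclear.

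The responder repeats raise a related but smaller point. Membership is decided at a scan after treatment starts, while the clock starts at first infusion.

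**Working it through.** The documents give no figure for OS from diagnosis, so there is nothing of the plan's own to reproduce. All survival and lag inputs below are assumptions, shown as ranges.

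**1. Direction.** At each death time the Kaplan-Meier factor is 1 − d/n. Ordinary and delayed-entry estimates share the same deaths d, but the ordinary n also includes subjects not yet infused. Each ordinary factor is therefore at least as large, and the ordinary curve is never below the delayed-entry curve on the same data.

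**2. Size, exponential model.** Let T be survival from the origin (rate a = ln 2 / true median) and L the lag to infusion (rate b = ln 2 / median lag in the whole diagnosed population), independent, with complete follow-up. Subjects are seen only if T > L, and ordinary Kaplan-Meier estimates

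S(t | T > L) = [(a + b)·e^(−at) − a·e^(−(a+b)t)] / b.

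Example: true median 36, lag 12 months. Then a = 0.01925, b = 0.05776, a + b = 0.07702. At t = 50.2 this is (0.07702 × 0.3804 − 0.01925 × 0.0209) / 0.05776 = 0.50, so the apparent median is 50.2 months, 39.5% too long.

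| Median lag (months) | True 24 | True 36 | True 60 |
|---|---|---|---|
| 3 | 28.1 (+17%) | 40.2 (+12%) | 64.2 (+7%) |
| 6 | 31.5 (+31%) | 44.0 (+22%) | 68.2 (+14%) |
| 12 | 36.6 (+53%) | 50.2 (+40%) | 75.6 (+26%) |
| 36 | 45.8 (+91%) | 63.8 (+77%) | 95.3 (+59%) |

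Protocol 4.1 admits newly diagnosed metastatic patients, whose lag is near zero. If half the population has zero lag and the rest a median of 12 to 36 months, the inflation is 12% to 26%.

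From initial diagnosis, with true medians of 60 to 156 months, the same formula gives 5% to 26% at lags of 6 to 12 months and 21% to 100% at 24 to 120 months. The 156 is the exponential median implied by 45% at 15 years: 180 × ln 2 / 0.7985.

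**3. Rising hazard.** The rates in Protocol 1.1 do not fit a constant hazard. Cumulative hazards −ln(0.80), −ln(0.60) and −ln(0.45) are 0.223, 0.511 and 0.799. The implied Weibull shape is ln(0.511/0.223)/ln 2 = 1.19 from years 5 and 10, and ln(0.799/0.223)/ln 3 = 1.16 from years 5 and 15. With S(t) = exp[−ln 2·(t/median)^1.2] and exponential lag, solve for 0.5:

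[S(t)(1 − e^(−bt)) + ∫ from t to ∞ of S(u)·b·e^(−bu) du] / ∫ from 0 to ∞ of S(u)·b·e^(−bu) du.

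| True median, lag (months) | Exponential | Shape 1.2 |
|---|---|---|
| 36, 12 | +40% | +28% |
| 156, 24 | +21% | +14% |
| 156, 60 | +44% | +31% |
| 60, 120 | +100% | +69% |

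The inflation is about 30% smaller in relative terms in these four cases.

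**4. Delayed entry as a repair.** It recovers the true median if lag and survival are independent. With a Gaussian-copula correlation of −0.3 / +0.3 and a true median of 36, it gives 39.5 / 30.2 at lag 3, 45.2 / 22.5 at lag 12 and 49.3 / 19.3 at lag 24. Ordinary Kaplan-Meier gives 41.6 / 38.7, 52.6 / 47.3 and 61.6 / 54.8: too long in all six cases. Delayed entry is also imprecise. At n = 42, true median 24, mean lag 12 and follow-up of 6 to 36 months, the 10th to 90th percentile range of its median is 14.9 to 33.6.

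**5. Responder subset.** Week 8 is 56 / 30.4375 = 1.84 months. Suppose PR carries no information on outcome and event times are exponential. Requiring survival to the response scan lengthens the median by 1.8 months if all responses fall at week 8, by about 2.7 if they are spread equally over weeks 8 and 16, and by 3.4 to 3.65 over weeks 8, 16 and 24. These shifts are against a cohort with no scan requirement. Against the Efficacy Evaluable set, itself conditional on the first scan (assumed at week 8), the OS shifts fall by 1.84, to 0, 0.9 and 1.8 months. The PFS shift is unchanged only if nobody dies before the first assessment.

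**The case against.** The other side has a good deal to say. The study is non-comparative and exploratory, no external comparison is planned, and no decision rests on these curves. The SAP states the origins openly and will report the lags in 7.4.3. The resection figures in Protocol 1.1 concern a different population, so that comparison would fail even without truncation. The table and figure templates that SAP section 4 mentions are not in the text reviewed, so suitable footnotes may already exist there. All of this stands and keeps the point minor. It does not make the estimate correct as SAP 7.5.3.3 describes it.

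The size objection also stands. Constant hazard overstates the effect, and the 100% case requires two-thirds of patients to die before infusion. The lags in the tables are population values; the lags among treated subjects in 7.4.3 cannot be read straight against them.

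On the responder repeats, SAP 7.5.3 uses sensitivity analysis for alternative analysis sets, and the Per-Protocol and Safety repeats change the population too. A changed population is therefore not the fault. The reason to relabel is selection on a later efficacy outcome that itself requires the subject to be alive. A reader might infer that these curves are invalid. They are not: they properly describe patients who had a PR.

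A reader might also infer that the main OS result is undermined. Its clock starts at first infusion. The Efficacy Evaluable set adds a guaranteed period of at most about 1.8 months if the first scan is at week 8, and the planned Safety-set repeat already covers that.

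**Conclusion.** As written, the diagnosis-origin OS analyses are wrong if read as survival from diagnosis. With independent lag, the ordinary curve overstates survival wherever there is a lag. It did so in the dependent scenarios computed as well, although dependence removes the general guarantee. The size cannot be fixed from the documents. Roughly 7% to 31% on the median at population lags of 3 to 6 months, and more beyond, is an exponential illustration, and a rising hazard makes it smaller.

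A reader might infer that the sponsor means to claim longer survival than historical patients. The documents do not support that: no such comparison is planned. The responder repeats are a secondary labelling point. Primary ORR, sample size and error rates are untouched. Severity: minor.

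**What to change.** 1. In SAP 6.4.1.2 and 7.5.3.3, either drop the two diagnosis-origin curves, or keep them with the label *conditional on surviving to first infusion; not comparable with published survival from diagnosis*. Call them additional, not sensitivity, analyses in both places.
2. Optional, only if an unconditional estimate is wanted: delayed-entry Kaplan-Meier in the Safety set, with entry at first infusion and numbers at risk shown. State that it needs entry time independent of survival. That is doubtful, because Protocol 4.1 requires progression within 6 months of consent or newly diagnosed metastatic disease.
3. In SAP 7.5.3.2 and 7.5.3.3, label the PR-subset repeats as descriptive of responders and not a test of the main result.
4. If DOR is to serve as the response-anchored outcome, time its landmarks from response. SAP 6.4.1.2 starts DOR at initial response, but SAP 7.5.3.1 counts its 2-, 4-, 6- and 8-month landmarks from the start of investigational product.

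The cost is a few lines of SAP text and footnotes, with no new data. The price is fewer, or less flattering, supplementary curves. Delayed entry, if chosen, brings small early risk sets and can err in either direction when lag and survival are related.
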